How often does it happen?		Red spots on your skin or bruises for no reason	
Nails		Hair	
Brittle nails		Hair loss	
Have you recently performed any cosmetic treatment on your nails?		Brittle hair Is your hair dyed or undergoing any cosmetic treatment?	

Table SM3.1 Continuation: Initial Assessment Questionnaire

Clinic history		
Signs and symptoms of nutritional deficiencies		
Mouth	Sueño	
Cuts at the corners of your mouth	How many hours do you sleep a day?	
How often does it happen?	Do you rest at night?	
Tongue swelling	Do you wake up during the night?	
How often does it happen?	How often does it happen?	
Gum inflammation	How many hours do you sleep a day?	
How often does it happen?	Do you rest at day?	
Solar exposition		
How many minutes do you expose yourself to the sun per day?	Do you cover your skin with long-sleeved clothing, pants, a cap or a hat?	
Less than 5 minutes	Always	
5 to 10 minutes	Sometimes	
10 to 15 minutes	Never	
15 to 20 minutes	Do you use sunscreen?	
20 to 30 minutes	Yes	
30 minutes to 1 hour	No	
More than 1 hour	How many days do you expose yourself to the sun per week?	
	1	
	2	
	3	
	4	
	5	
	6	
	7	
Lactation	Write for how long	
Exclusive breastfeeding		
Formula feeding (if you received only artificial milk as food)	Observations:	
Mixed breastfeeding (if in addition to breastfeeding you received any artificial milk)		
Supplemented breastfeeding (if non-dairy solid or liquid foods were received in addition to breastfeeding)		
Mixed supplemented breastfeeding (if it was a breastfed infant, who also received some artificial milk and solid or liquid foods)		
Complemented artificial feeding (if when breastfeeding you received artificial milk and solid or liquid foods)		
Festivities		
Please write the main holidays you celebrate and on the right side write the main foods you eat on these holidays		
Festivity	Food eaten on the holiday	
Hygiene habits		
How often do you take a bath?		
How many times do you brush your teeth a day?		
Is the street where you live paved?		
What type of flooring does your house have?		
Do you have pets? What type?		

Table SM3.1 Continuation: Initial Assessment Questionnaire

Table SM3.1 Continuation: Initial Assessment Questionnaire

24-hour reminder			
Food time	Menu / Preparation	Ingredient / Food	Quantity
Breakfast			
Hour:			
Place:			
Morning snack			
Hour:			
Place:			
Meal			
Hour:			
Place:			
Evening snack			
Hour:			
Place:			
Dinner			
Hour:			
Place:			
Milliliters of water consumed throughout the day:			

Table SM3.1 Continuation: Initial Assessment Questionnaire

Food frequency questionnaire																									

For each food, indicate how many times per month or per week you consume it. Subsequently, indicate how many times a day you consume it, the day you take it. For example, if you drink 2 cups (480 milliliters) of whole milk 3 times a week and those 3 days you drink it in the morning and at night, you drink it 3 times a week and 2 times a day, in a quantity of 2 portions. It is also important to consider the summer/winter variation. For example, if you eat ice cream 4 times a week during the 3 summer months, your average consumption is 1 time a week.
																									
Group	Food	Portion	Type, brand, flavor or preparation	Average consumption last year							When you consume it, how many times a day do you do it? (Check 1 option per day)	Number of servings													
				Times a year			Times a month		Times a week			Times a day		(Mark how many servings you consume each time you eat it)											
				Never	1-5	6-11	1	2	3	1		2	3	4	5	6	7	1	2	3	4+	1/4	1/2	1	2
Dairy	1. Whole milk	1 cup (240 ml)																							
	2. Semi-skim milk	1 cup (240 ml)																							
	3. Skim milk	1 cup (240 ml)																							
	4. Almond milk	1 cup (240 ml)																							
	5. Soy milk	1 cup (240 ml)																							
	6. Coconut milk	1 cup (240 ml)																							
	7. Chocolate flavored milk	1 cup (240 ml)																							
	8. Packaged milk shake	1 cup (240 ml)																							
	9. Whole yogurt (sweetened with fruit)	1 cup (227 g)																							
	10. Low-fat yogurt	1 cup (240 g)																							
	11. Fermented milk drink	1 piece (80 g)																							
	12. Bionico cream (evaporated milk with cow cream)	½ cup (120 g)																							
Cheeses	13. Curd	3 tablespoons (42 g)																							
	14. Cottage cheese	3 tablespoons (48 g)																							
	15. Fresh cheese (not in quesadillas)	1 slice (40 g)																							
	15.1 Panela cheese (not in quesadillas)	1 slice (40 g)																							
	16. Cured cheeses consumed alone (manchego, oaxaca, asadero, mozzarella, cheddar, goat, parmesan, chihuahua), (not in quesadillas)	1 slice (30 g)																							
Animal source foods	17. Chicken eggs	1 piece (60 g)																							
	18. Egg white	2 pieces (66 g)																							
	19. Chicken with skin (chicken pieces except wings)	1 piece (200 g)																							
	20. Chicken without skin in pieces	1 piece (200 g)																							
	20.1 Grilled skinless chicken fillet	1 ration (90 g)																							
	21. Turkey	1 ration (108 g)																							
	21.1 Bunny	1 ration (90 g)																							
22. Beef steak or steak (stews, griddle)	1 ration (90 g)																								

Note: foods colored blue corresponds to those that will be included in the intervention program and correspond to those presented in Table A6.5, where the frequency and quantity of consumption to be promoted are specified. FCFQ adapted from: [name]; [name]; [name]; [name] Nutrieccology: A Mexican web-based nutritional ecologic software for the assessment of diet, dietary pattern, diet quality, and dietary environmental impact. Nutrients (under revision).

Supplementary Material 4. COM-B questionnaire including nutritional-sustainable knowledge questions

This questionnaire will be modified based on the issues addressed during the development of the program, as well as based on the execution of the pilot test, where multiple options will be established for data analysis. However, the format to be used and the questions determined so far are presented below, which incorporate the elements of the COM-B model, which include capacity, opportunity, and motivation (14). Likewise, questions on sustainable food consumption were integrated, according to the questionnaire by Verain et al. (62).

Table SM4.1. COM-B questionnaire including nutritional-sustainable knowledge questions

COM-B questionnaire						
Participant number:						
Date:						
COM-B dimension	Answer		Mark your answer	Explain your answer		
Capability						
Knowledge of general nutrition and sustainability						
Do you know which food groups exist?	Yes					
	No					
	If you know, write them down please.					
Do you know what foods contain carbohydrates?	Yes					
	No					
	If you know, write them down please.					
Do you know what foods contain fat?	Yes					
	No					
	If you know, write them down please.					
Do you know what foods contain protein?	Yes					
	No					
	If you know, write them down please.					
Did you know that the food you eat requires high amounts of water during its production?	Yes					
	No					
	Explain your answer please					
Did you know that the food you eat generates greenhouse gas emissions during its production, which promote climate change?	Yes					
	No					

	Explain your answer please	
What foods do you think use more water during their production?	Yes	
	No	
	If you know, write them down please.	
What foods do you think generate more greenhouse gas emissions during their production?	Yes	
	No	
	If you know, write them down please.	
Do you consider that the traditional Mexican diet is healthy?	Yes	
	No	
	Explain your answer please	
Do you consider that the tortilla is "fattening"?	Yes	
	No	
	Explain your answer please	
Do you consider that buying food in local markets or markets is frowned upon?	Yes	
	No	
	Explain your answer please	
Do you consider it a better option to buy your food in supermarkets than in local markets?	Yes	
	No	
	Explain your answer please	
If you knew all the environmental impacts of your diet, would you change it?	Yes	
	No	
	Explain your answer please	
Would you be willing to eat less red meat if you knew that it had a high environmental impact?	Yes	
	No	
	Explain your answer please	
Do you know what sustainable diets are?	Yes	
	No	
	Explain your answer please	
Specific nutrition and sustainability knowledge		
Aspect	Write your answer please	
Please mention the benefits of physical activity		
Mention what is the recommended amount of physical activity to perform per day		
Please mention the benefits of consuming a traditional Mexican diet		
Mention what is the recommended amount to consume of portions of Mexican food per day		
Please mention the benefits of consuming fruits and vegetables		
Mention what is the recommended amount to consume of servings of fruits and vegetables per day		
Please mention the benefits of consuming whole grains		
Mention what is the recommended amount to consume of servings of whole grains per day		
Please mention the benefits of consuming legumes		
Mention what is the recommended amount to consume portions of legumes per day		
Please mention the benefits of consuming seeds and healthy fats		
Mention what is the recommended amount to consume of portions of seeds and healthy fats per day		
Please mention the benefits of consuming dairy in adequate amounts		
Mention what is the recommended amount to consume of dairy portions per day		

Please mention the benefits of consuming eggs in adequate amounts	
Mention what is the recommended amount to consume of servings of eggs per day	
Please mention the benefits of consuming fish and shellfish in adequate amounts	
Mention what is the recommended amount to consume of portions of fish and shellfish per day	
Please mention the benefits of consuming chicken in adequate amounts	
Mention what is the recommended amount to consume chicken portions per day	
Please mention the benefits of avoiding red and processed meats	
Mention what is the recommended amount to consume of portions of red and processed meats	
Please mention the benefits of avoiding ultra-processed foods	
Mention what is the recommended amount to consume of portions of ultra-processed foods per day	
Please mention the benefits of avoiding added sugar, foods high in trans and saturated fats	
Mention what is the recommended amount to consume of portions of added sugar, foods high in trans and saturated fats	
Food preparation skills	
Do you know how to cook?	Yes / No
If the answer was yes, what foods do you know how to cook?	
Preparation capacity	
Does it have a kitchen equipped with a stove?	Yes / No
Does it have a kitchen equipped with a refrigerator?	Yes / No
Does it have a kitchen equipped with an oven?	Yes / No
Opportunity	
Time to eat	
How many minutes a day do you have for breakfast?	
How many minutes a day do you have to eat?	
How many minutes a day do you have for dinner?	
How many minutes a day do you have to consume snacks?	
Prepare food	
How many minutes a day do you have to prepare your breakfast?	
How many minutes a day do you have to prepare your food?	
How many minutes a day do you have to prepare your dinner?	
How many minutes a day do you have to prepare your snacks?	
Access to food	
Are there places selling fresh food (fruits, vegetables) near your home?	Yes / No / I do not know
Are there non-perishable food outlets near your home (beans, oatmeal, rice, crackers, etc.)?	Yes / No / I do not know
Food storage	
Do you have a refrigerator at home?	Yes / No
Do you have containers to store food (tupers)?	Yes / No
Motivation	
You want to change your eating habits	
Would you like to improve your eating habits?	Yes / No / I do not know
Would you like to eat healthier?	Yes / No / I do not know
Would you like to be a more physically active person?	Yes / No / I do not know
Emotions involved in your food consumption	

Do you eat more food or less food when you are sad, angry, or happy?	Please specify the emotion and the effect it has on your hunger and satiety					
Habits you are willing to change						
Please write down the eating habits that you would be willing to change, for example, eat more fruits and vegetables, eat less beef, etc.						
Reasons for sustainable food consumption						
Please write how important the following aspects are to you when you are going to consume food 1 is not very important and 5 is very important						
Animal welfare						
Produced without animals suffering	(Not very important)	1	2	3	4	5 (Very important)
Produced in an animal-friendly way	(Not very important)	1	2	3	4	5 (Very important)
It is produced respecting the rights of animals	(Not very important)	1	2	3	4	5 (Very important)
Produced with enough space for animals	(Not very important)	1	2	3	4	5 (Very important)
It is a free range or free range product	(Not very important)	1	2	3	4	5 (Very important)
Ethical concern						
Produced without exploitation	(Not very important)	1	2	3	4	5 (Very important)
Produced without child labor	(Not very important)	1	2	3	4	5 (Very important)
Traded fairly	(Not very important)	1	2	3	4	5 (Very important)
Environmental welfare						
Produced in an environmentally friendly way	(Not very important)	1	2	3	4	5 (Very important)
It is produced without disturbing the balance of nature	(Not very important)	1	2	3	4	5 (Very important)
Produced with minimal CO2 emissions	(Not very important)	1	2	3	4	5 (Very important)
It is packaged in an environmentally friendly way	(Not very important)	1	2	3	4	5 (Very important)
Local and seasonal						
It is a local/regional product	(Not very important)	1	2	3	4	5 (Very important)
It is a seasonal product	(Not very important)	1	2	3	4	5 (Very important)
It comes from nearby (short transport distance).	(Not very important)	1	2	3	4	5 (Very important)

Supplementary Material 5. Primers for bacteria identification in the qPCR analysis

Bacteria	Name	Primer (5'-3')	Number of bases	Sequence	Notes	Reference
Firmicutes	928F-Firm	Forward	21	5'-TGAAACTCAAAGGAATTGACG-3'	Y = C or T → C	
	1040FirmR	Reverse	17	5'-ACCATGCACCACCTGTC-3'		
Bacteroidetes	798cfbF	Forward	20	5'-CAAACAGGATTAGATACCT-3'	R = A or G → A	
	Cfb967R	Reverse	19	5'-GGTAAGGTTCTCGCGTAT-3'		(4,68)
Universal	926F	Forward	20	5'-AAACTCAAAGGAATTGACGG-3'	K = G or T → G	
	1062R	Reverse	18	5'-CTCACAAACACGAGCTGAC-3'	R = A or G → A	
Lactobacillus		Forward	19	5'-AGCAGTAGGGAATCTTCCA-3'		
		Reverse	17	5'-CACCGCTACACATGGAG-3'		
Bifidobacterium		Forward	18	5'-TCGCGTCCGGTGTGAAAG-3'	C	
		Reverse	17	5'-CCACATCCAGCATCCAC-3'	A	
Faecalibacterium prausnitzii	FPR-2F	Forward	19	5'-GGAGGAAGAAGGTCTTCGG-3'	Amplicon 248	
	Fprau645R	Reverse	21	5'-AATTCCGCCTACCTCTGCACT-3'		(73)
Akkermansia muciniphila		Forward	20	5'-CAGCACGTGAAGGTGGGGAC-3'		
		Reverse	20	5'-CCTTGCCTGGCTTCAGAT-3'		(74)
Prevotella copri		Forward	20	5'-CCGGACTCCTGCCCTGCAA-3'		
		Reverse	20	5'-GTTGCGCCAGGCAGTGCAT-3'		(75)
Bilophila wadsworthia		Forward	26	5'-CAACGTCCCCACCATCAAGTTCTTG-3'		
		Reverse	26	5'-TGAATTGCGGAAGGAGCGAGAGGTC-3'		(77)
Clostridium coccoides		Forward	19	5'-CGGTACCTGACTAAGAACG-3'	429 pb	
(Eubacterium rectale group and Lachnospiraceae family)		Reverse	19	5'-AGTTTCATTCTTGCAG-3'	429 pb	(48)
Streptococcus thermophilus	St1	Forward	22	5'-TTATTGAAAGGGCAATTGCT-3'	Posición: 195-216	
	St2	Reverse	21	5'-GTGAACCTTCCACTCTCACAC-3'	Posición: 474-454	(80)

Bases modified according to "Re: What are Y, M, W and D in primer design?", by A. Gund, Nadine, 2014. https://www.researchgate.net/post/What_are_Y_M_W_and_D_in_primer_design/538c1577d11b8ba27a8b45df/citation/download.

Supplementary Material 6. Adherence questionnaire

This questionnaire will be updated based on the food plans to be designed, so the recommendations provided, and the consumption of the population will be contrasted, after the pilot test of this study. However, the format to be used and the questions developed so far are presented below.

Table SM6.1. Questionnaire of adherence to the sustainable-psycho-nutritional program

Questionnaire of adherence to the sustainable-psycho-nutritional program								
Participant number:								
Date:								
Questions about food consumption	Times per week							Times per day
	1	2	3	4	5	6	7	
How many times a week do you eat foods that include corn?								
How many times a week do you eat foods that include amaranth?								
How many times a week do you eat fruit?								
How many times a week do you eat vegetables?								
How many times a week do you eat foods that include beans?								
How many times a week do you eat foods that include lentils?								
How many times a week do you eat foods that include canola, olive, or avocado oil?								
How many times a week do you eat foods that include milk?								
How many times a week do you eat foods that include cheese?								
How many times a week do you eat foods that include yogurt?								
How many times a week do you eat foods that include eggs?								
How many times a week do you eat foods that include fish or shellfish such as shrimp, octopus or crab?								
How many times a week do you eat foods that include chicken?								
How many times a week do you eat foods that include beef or red meat such as pork, lamb, and goat?								
How many times a week do you eat foods that include processed meats like ham and sausage?								
How many times a week do you consume soft drinks?								
How many times a week do you eat packaged (ultra-processed) foods?								
Question about consumption reasons	Answers							
Have you ever preferred to eat a particular food because of its environmental impact?	Yes	No	Explain your answer please:					
Have you ever preferred to eat a particular food because of its impact on health and nutrition?	Yes	No	Explain your answer please:					
From 1 to 10, how much would you say you consumed the meal plan that was provided to you?	Yes	No	Explain your answer please:					
Was there any food that you did not like and therefore did not consume it?	Yes	No	Explain your answer please:

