Step 4: Identify what needs to change	
 1. Increase physical activity. 2. Increase the consumption of sustainable Mexican foods and dishes. 3. Increase the consumption of fruits and vegetables. 4. Increase the consumption of whole grains. 5. Increase the consumption of legumes. 6. Increase the intake of seeds and healthy fats. 7. Reduce dairy consumption. 8. Reduce the consumption of eggs. 9. Reduce consumption of fish and shellfish. 10. Reduce chicken consumption. 11. Reduce the consumption of red (beef, pork, goat, and lamb) and processed meats. 12. Reduce the consumption of ultra-processed foods. 13. Reduce the intake of added and free sugars, as well as foods with a high content of trans and saturated fats. 
All foods whose consumption will be promoted will be aligned with the sustainability characteristics for the Mexican context (12), on the recommendations of a healthy diet provided by the WHO (35), and on the model QC7G for food and nutrition education, that will specify which foods to select, in which quantities, when to consumed them and how to prepare them. In addition to when to perform physical activity, specifying type and duration (13).

Stage 2: Identify intervention options	
Step 5: Intervention functions	The intervention functions from the behavior change wheel model will be: education, persuasion, incentivization, and coercion. These will be verified in relation to the APEASE criterion Michie et al. (36).

Table 1. Continuation: Design of the Sustainable-Psycho-Nutritional intervention program according to the behavior change wheel model and guide for interventions design

Stage 2: Identify intervention options	

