	10 to 29 minutes of each	Intense	8
	30 to 59 minutes of each	Intense	16
	60 to 120 minutes of each	Intense	24
	More than 120 minutes, but less than 240 minutes of each	Intense	32
	More than 240 minutes of each	Intense	32 points and send a message not to exceed the amount of exercise

Table SM1.3. Scores according to the frequency of food consumption by groups

Food group	Points for consumption frequency	Score
Mexican food and dishes	Once a week	1
	2 times a week	2
	3 times a week	3
	4 times a week	4
	5 times a week	5
	6 times a week	6
	7 times a week	7
	< once a week	0
Mexican desserts and drinks	Once a week	1
	2 times a week	0
	3 times a week	0
	4 times a week	0
	5 times a week	0
	6 times a week	0
	7 times a week	0
	Once a week	1
Fruits, vegetables, legumes, dairy, seeds and healthy fats, eggs	2 times a week	2
	3 times a week	3
	4 times a week	4
	5 times a week	5
	6 times a week	6
	7 times a week	7
	< once a week	0
	Once a week	3
Fish and shellfish, chicken and other white meats	2 times a week	2
	3 times a week	1
	4 times a week	0
	5 times a week	0
	6 times a week	0
	7 times a week	0
	0 times a week	7
	Once a week	1
Red and processed meats, Ultra-processed foods, Foods high in sugars, trans and saturated fats	2 times a week	0
	3 times a week	0
	4 times a week	0
	5 times a week	0
	6 times a week	0
	7 times a week	0
	Once a week	1

Table SM1.4. Scores by frequency of consumption

Food group	Consumption quantities	Score
Mexican foods and dishes, fruits, vegetables, legumes, dairy products, seeds and healthy fats, eggs	< recommended portion or > minimum portion	1
	Recommended portion	2
	< recommended maximum or > recommended portion	1
	> the recommended maximum or < the recommended minimum	0
Fish and shellfish, chicken and other white meats, Red and processed meats, Ultra-processed foods, Foods high in sugars, trans and saturated fats	Minimum portion	3
	< Recommended portion > minimum portion	2
	> recommended portion < maximum portion	1
	> Maximum portion	-1

Note: recommend amount of consumption will be determined by the linear optimization programming. An example is shown in Table SM1.5.

Table SM1.5. Examples of recommended amounts of consumption by food groups including the target foods of the intervention

Consumption	Group by objective	Food	Examples of amounts of consumption		
			Average Recommended Serving	Range	Minimum

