Note: this table will be updated according to the linear optimization programming.

Supplementary Material 2. Inclusion, exclusion, and elimination criteria

Table SM2.1. Inclusion, exclusion, and elimination criteria

Study Criteria		
Inclusion	Exclusion	Elimination
Being between 18 and 35 years old	Not signing the informed consent	Not completing the questionnaires
Being Mexican	Not accepting to donate blood and/or stool samples	Do not allow the extraction of blood and / or delivery of stool sample
Reside in the South of Jalisco for at least 1 year	Not being able to stand up to take anthropometric data	Failure to complete the 7-week intervention or 7-week follow-up
Levels of physical activity below what is recommended and what is established as a criterion for inclusion in the study (Table SM2)	Perform levels of physical activity above the minimum established as criteria for inclusion in the study (Table SM2)	
Consuming amounts of food below or above that established as criteria for inclusion in the study or in a lesser or greater frequency than recommended, according to the type of food (Table SM2)	Consume adequate levels of the foods to be promoted in the intervention program (Table SM2)	
Have a Smartphone	Being pregnant or lactating	
Not having consumed antibiotics at least 3 months before the intervention	Suffer from a chronic disease such as type 2 diabetes mellitus, arterial hypertension, dyslipidemia, under medication	
Have a BMI between 18.5 and 40	Suffering from an autoimmune disease such as type 1 diabetes, hypo or hyperthyroidism	
Not having a medical diagnosis of chronic disease under pharmacological treatment	Having a gastrointestinal disease such as Crohn's disease, ulcerative colitis, etc.	
Not having a medical diagnosis of gastrointestinal disease	Having used antibiotics less than 3 months ago	
	Taking antidepressant medications or corticosteroids	
	Consume probiotics or nutritional supplements, except protein powder	

Table SM2.2 Cut-off points to establish inadequate consumption and physical activity, to be included in the research

Physical activity	Inclusion criteria	
	Light	
	< 3 times per week	< 30 minutes per day
Type of physical activity		
Weekly frequency		
Minutes per day		
Food group	Consumption to be included in the study	Frequency of consumption to be included in the study
Mexican food and dishes	< 100 g p ⁻¹ d ⁻¹	< 7 times a week
Fruits	< 400 g p ⁻¹ d ⁻¹	< 7 times a week
Vegetables	< 400 g p ⁻¹ d ⁻¹	< 7 times a week

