Whole cereals	< 200 g p ⁻¹ d ⁻¹	< 7 times a week
Legumes	< 60 g p ⁻¹ d ⁻¹	< 7 times a week
Seeds and healthy fats	< 80 g p ⁻¹ d ⁻¹	< 7 times a week
Dairy products	> 250 ml p ⁻¹ d ⁻¹	> 5 times a week
Eggs	> 25 g p ⁻¹ d ⁻¹	> 5 times a week
Fish and shellfish	> 28 g p ⁻¹ d ⁻¹	> 3 times a week
Chicken	> 29 g p ⁻¹ d ⁻¹	> 3 times a week
Red and processed meats	> 7 g p ⁻¹ d ⁻¹	> once a week
Ultra-processed foods	> 10 g p ⁻¹ d ⁻¹	> once a week
Added and free sugars and foods high in trans and saturated fats	> 31 g p ⁻¹ d ⁻¹	> once a week

Supplementary Material 3. Clinical history which will be uploaded to the mobile application

Table SM3.1 Initial Assessment Questionnaire

Clinic history				
General and sociodemographic data				
Last name:	Middle name:	Name:		
Cell phone:	Email:			
Age:	Date of Birth:			
Sex:	Country of birth:			
City of residence:	State of birth:			
Time living there:	Occupation			
Less than 1 month	Officer, director or boss			
1 to 6 months	Professional or technician			
6 to 12 months	Auxiliary worker in administrative activities			
1 to 3 years	Merchant, sales clerk, or sales agent			
3 to 6 years	Workers in personal and surveillance services			
6 to 9 years	Worker in agricultural, livestock, forestry, hunting or fishing activities			
10 years or more	Craft worker			
Lifetime	Industrial machinery operator, assemblers, chauffeur or transport driver			
	Workers in elementary and support activities			
Education				
Did not study	Student			
Unfinished primary	Unemployed			
Finished elementary school	Retired			
Unfinished high school	Other (specify):			
High school finished	Days a week that work			
Unfinished high school	1			
School completed	2			
Unfinished technical career	3			
Technical career finished	4			
Undergraduate student	5			
Unfinished degree	6			
Completed bachelor's degree	7			
Master's degree	Modality			
Doctorate	Face-to-face			
Specialty	Online			
Other:	Mixed			
Individual and family monthly income (pesos per month MXN)	Individual expenditure on food per month (MXN pesos)	Household expenditure on food per month (MXN pesos)	Feeding	
-0 - 2,699		0 - 500	Favorite foods	
2,7 - 0 - 6,799	-0 - 200	500 - 1,000		
6,8 - 0 - 11,599	2-0 - 500	1,000 - 3,000	Foods you don't like	
11,6 - 0 - 34,999	500 - 800	3,000 - 6,000		
35,000 - 84,999	800 - 1,000	6,000 - 9,000	Food allergies and intolerances	
+ 85,000	1,500- 2,000	10,0-0 - 13,000	Lactose	
	2,500 - 3,000	13,000 - 16,000	Seafood	
	3,000 - 3,500	16,000 - 20,000	Gluten	

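### The plan contradicts itself on dairy and egg frequency: both are to be reduced and more than 5 times a week counts as inadequate, yet the SM1.3 token points peak at 7 times a week

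*Combined protocol and SAP*

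**What the plan says.** **Targets.** Among the 13 objectives in Table 1 (section 2.1.2) are "7. Reduce dairy consumption. 8. Reduce the consumption of eggs", followed by "9. Reduce consumption of fish and shellfish. 10. Reduce chicken consumption".

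**Entry cut-offs.** Table SM2.2 is titled "Cut-off points to establish inadequate consumption and physical activity, to be included in the research". For dairy it gives more than 250 ml a day and "> 5 times a week"; for eggs, more than 25 g a day and the same frequency. Table SM2.1 links amount and frequency with "or in a lesser or greater frequency than recommended, according to the type of food", so frequency alone can count as inadequate.

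**Token points for frequency.** Table SM1.3 scores dairy and eggs in the row "Fruits, vegetables, legumes, dairy, seeds and healthy fats, eggs". That row gives one point per weekly occasion up to 7 at 7 times a week, and 0 below once a week.

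**Token points for portion.** Table SM1.4 again groups dairy and eggs with the promoted foods: 2 points at the recommended portion, 1 on either side of it within the allowed range, and 0 above the maximum or below the minimum.

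**Recommended intake.** Table SM1.5 lists dairy and eggs as separate groups, each to be eaten daily. Example servings are 240 ml of milk and a 44 g egg. A note says the table will be revised after the linear programming.

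Section 2.1.1 says that the Supplementary Material 1 scores go into the app. Table 1, Step 7, places the token economy under incentivization, coercion and monitoring.

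**The concern.** The two frequencies that SM1.3 pays best for dairy and eggs, 6 and 7 times a week, are the two that SM2.2 calls inadequate. A participant who enters the study eating eggs every day could collect the top frequency score for eggs without changing anything, and collect less after cutting back. The frequency points would then pull against 2 of the 13 stated objectives.

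The other foods to be reduced are handled differently. The SM1.3 row "Fish and shellfish, chicken and other white meats" has an SM2.2 cut-off of "> 3 times a week" and pays 0 from 4 times a week. Red and processed meats have a cut-off of more than once a week and pay 0 from 2 times.

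At stake is whether this part of the intervention carries a consistent message. The plan does not say whether a daily dairy or egg eater is on target.

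**Working it through.** **1. SM1.3 against SM2.2.** The alignment of row labels in the text is loose by one line, but the scores for 2 to 7 times a week rise under any plausible alignment.

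| SM2.2 food groups | SM2.2 inadequate at | SM1.3 points | Agree? |
|---|---|---|---|
| Mexican foods, fruits, vegetables, legumes, seeds/fats (5) | < 7 a week | peak at 7 | yes |
| Fish, chicken (2) | > 3 a week | 0 from 4 | yes |
| Red/processed meats, ultra-processed, sugars/fats (3) | > 1 a week | 0 from 2 | yes |
| Dairy, eggs (2) | > 5 a week | 6 at 6, 7 at 7 | no |

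Taken at face value, 10 of the 12 SM2.2 food groups named in SM1.3 agree. The thirteenth, whole grains, is not named there, which is a separate matter.

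**2. Frequency points alone.** Assume each food is scored separately. Going from 7 to 5 times a week gives 5 − 7 = −2, that is 2 of 7 points per food, or 4 for both foods. If the shared row is instead scored once and any food in it counts, cutting dairy or eggs need cost nothing.

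**3. Adding the SM1.4 portion points.** Let p0 and p1 be the portion scores (0, 1 or 2) before and after cutting from 7 to 5 times a week. The plan does not say whether portions are scored once a week or at each occasion.

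- Weekly: net = (5 + p1) − (7 + p0)
- Per occasion: net = (5 + 5·p1) − (7 + 7·p0)

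| p0 → p1 | Weekly | Per occasion |
|---|---|---|
| 0 → 0 | −2 | −2 |
| 1 → 1 | −2 | −4 |
| 2 → 2 | −2 | −6 |
| 0 → 1 | −1 | +3 |
| 1 → 2 | −1 | +1 |
| 0 → 2 | 0 | +8 |

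With an unchanged portion score the net is always negative. When an oversized portion also shrinks, it runs from −1 to 0 (weekly) or +1 to +8 (per occasion). The best attainable total is still at 7 times a week: 7 + 2 = 9 against 5 + 2 = 7 (weekly), or 7 + 14 = 21 against 5 + 10 = 15 (per occasion).

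**4. Amounts.** One 240 ml milk serving a day is below the 250 ml cut-off, so daily dairy in that portion meets the amount limit. One 44 g egg a day exceeds 25 g. Reading the cut-off as a weekly average, five such eggs a week give 5 × 44 / 7 = 31.4 g a day, which is still above it.

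**5. Effect of paying 0 at 6 and 7 times a week,** keeping 5 points at 5 times and the portion score p unchanged:

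- Weekly: (5 + p) − (0 + p) = +5.
- Per occasion: (5 + 5p) − (0 + 7p) = 5 − 2p, that is +5, +3 or +1 for p = 0, 1 or 2.

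Cutting to 5 is then rewarded under either rule. With per-occasion scoring this needs more than 2 × 2 = 4 frequency points at 5 times a week.

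**The case against.** The strongest reply is that daily intake in moderate portions is what the plan intends, and that SM2.2 is the odd table out. SM2.2 is an eligibility screen, not a prescription. The tables that define what is promoted agree with one another: SM1.3 peaks at 7, SM1.4 groups dairy and eggs with the promoted foods, and SM1.5 lists both daily. To reduce can mean to reduce the amount, and the knowledge questionnaire in Supplementary Material 4 speaks of adequate amounts of both foods.

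Much of this stands. A reader might infer that SM1.3 is simply wrong, but the documents do not show that. The contradiction remains all the same, because SM2.2 flags frequency separately from amount, the egg amounts do not fit, and the questionnaire uses the same phrasing for fish and chicken, whose points fall with frequency. If daily intake is meant, SM2.2 and objectives 7 and 8 need the change instead.

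The contrast with the other foods is also less clean than the 10-of-12 count suggests. SM1.5's daily Mexican dishes include several made with chicken, and the plan does not say whether such a dish is also scored as chicken.

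Section 2.1.1 puts the cut-off points in the future, so they may still change. But the revision note belongs to SM1.5 and the linear-programming note under SM1.4 concerns amounts; neither covers the SM1.3 points.

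Finally, tokens are one technique among several, objectives are individually adapted (section 2.2.2), and a single exercise entry in SM1.2 can score 32. These facts limit the weight of the point without resolving it.

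**Conclusion.** The inconsistency is real, and its severity is minor. The documents establish that objectives 7 and 8 and the SM2.2 frequency cut-off point one way, and SM1.3 and SM1.5 the other. At a fixed portion, with foods scored separately, cutting from 7 to 5 times a week costs 2 of 7 frequency points per food. Separate scoring is an assumption: SM1.5's separate groups suggest it but do not settle it.

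Two stronger readings are tempting and not supported:

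- **That the token system as a whole penalises cutting back, or that nothing in it rewards reduction.** SM1.4 pays for bringing an oversized portion down, and the net change in the cases computed runs from −6 to +8 per food under scoring rules that are not stated.
- **That the trial's results are biased.** Section 2.3.4 names no token score and section 2.3.3 measures adherence by its own questionnaire. The point concerns the content of one intervention component, and its effect on intake cannot be estimated from the documents.

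**What to change.** Before the scores are loaded into the app, decide the intended weekly frequency for dairy and for eggs, then align the tables by one of two routes.

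**A. If the SM2.2 limit of 5 times a week is the target:** take dairy and eggs out of the promoted-food row of SM1.3, give 0 frequency points at 6 and 7 times a week (as SM1.3 already does above the cut-off for fish, chicken and red meat), and change the daily entry in SM1.5 to match. The nutrition team sets the points from 1 to 5 times a week so that the scale does not push intake below what it intends.

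**B. If moderate daily portions are the target:** keep SM1.3, remove the frequency cut-off for dairy and eggs from SM2.2, and reword objectives 7 and 8 as reducing portion size.

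Route B must reconcile the 44 g daily egg with the 25 g cut-off; under route A the egg serving deserves the same check. Under either route, state whether foods in a shared row are scored separately and whether portions are scored weekly or per occasion.

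The cost is a table edit and a check of the app rules, with no added participants, visits or procedures. Route B also changes an entry criterion, so it should be settled before screening.
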